6 STUDY INTERVENTION/INVESTIGATIONAL PRODUCT

6.1 Study Product Description

Ketorolac tromethamine is a member of the pyrrolo-pyrrole group of nonsteroidal anti-inflammatory drugs (NSAIDs) and supplied as a racemic mixture of [-]S and [+]R ketorolac tromethamine. Ketorolac tromethamine may exist in three crystal forms; all forms are equally soluble in water. Ketorolac tromethamine has a pKa of 3.5 and an n-octanol/water partition coefficient of 0.26. The molecular weight of ketorolac tromethamine is 376.41 and the molecular formula is C₁₉H₂₄N₂O₆.

6.1.1 Acquisition

Ketorolac tromethamine will be obtained by the pharmacy department from Hospira, Inc.

6.1.2 Formulation, Packaging, and Labeling

Ketorolac tromethamine is supplied as a 30mg/mL clear to slightly yellow sterile solution for injection in a 1mL single-dose vial. The solution contains 10% (w/v) alcohol.

6.1.3 Product Storage and Stability

Ketorolac tromethamine will be stored at room temperature (20-25 degrees Celsius) in its original container and protected from light. The product will be maintained securely by the pharmacy department and stored separately from the general stock.

6.2 Dosage, Preparation and Administration of Study Intervention/Investigational Product

Dosage

The dose of ketorolac is 0.5mg/kg given intravenously every 8 hours for 72 hours. The first dose will be given within 24hrs from the conclusion of the surgical procedure. A total of 9 doses will be administered.

Preparation & Blinding

Subjects will be assigned to treatment or placebo in sequential order as indicated by the provided randomization scheme. The pharmacy will then aseptically prepare the blinded syringe of investigational product. Ketorolac will be diluted with 0.9% Sodium Chloride to a

concentration of 0.6mg/mL. Subjects assigned to placebo will be given 0.9% Sodium Chloride at a volume equivalent to the active product.

All study syringes will be administered within 24 hours of preparation.

6.3 Modification of Study Intervention/Investigational Product for a Participant

Dose modifications will not be performed, as this drug will be administered on a weight-based calculation. Patients who experience a bleeding episode or acute change in renal function as defined previously (Section 5.2.3) will not have dose modification, but will be pulled from the study.

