5.3.3 Reasons for Withdrawal

Those who will monitor the data include the study staff physicians and pharmacist. The data to be monitored include any bleeding events, evaluation of renal function including BUN and Creatinine levels. These will be monitored on an individual patient basis at least daily. Additional outcomes as mentioned in primary and secondary outcomes section will be monitored.

Bleeding events: Bleeding events will be closely monitored in the NICU setting. Daily CBC's are obtained during the postoperative period, and these will be recorded as data relevant to the study. Deviations in hemoglobin or platelet counts will be detected, and treated as is standard of care.

Bleeding episodes will be defined by following:

1. Persistent bloody drainage from a nasogastric tube, resulting in a drop of hemoglobin of greater than or equal to 2g/dL (change of 1g/dL in hemoglobin may be explained by the infusion of perioperative crystalloid, and in the absence of hemodynamic instability would be considered within the acceptable standard deviation)
2. Surgical site bleeding resulting in a drop of hgb >2g/dL from initial postop value, unless the patient has required crystalloid or fluid boluses other than PRBC totalling 60ml/kg or greater.
3. Any hemodynamic instability associated with a drop of hemoglobin >2g/dL

Renal injury: Several published criteria for adults and children exist to enable the practitioner to identify early signs of renal injury (9-11). Of these, the Pediatric modification of the Risk, Injury, Failure, Loss, End-Stage Renal Disease (p-RIFLE) criteria are probably the most reliable in this population, as this has been validated in children.

Based upon these criteria, renal function will be monitored frequently. Based upon the following criteria, a patient will be unblinded and pulled from the study:

1. Patients who are resuscitated but with continued postoperative UOP<0.5ml/kg/h persistent over 8 hours
2. A decrease in estimated creatinine clearance by 25%, in a well-resuscitated patient

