5.3.4 Withdrawals

Subjects are free to withdraw from participating in the study at any time upon request.

The patient will become unblinded and pulled from receiving the study drug or placebo if any bleeding events occur or if renal function worsens (rise in greater than 0.5mg/dL). However, events will still be recorded on the patient, and these patients will still be followed for the duration of the study (i.e. 5 days or 72 hrs from the end of the study drug), or until resolution and or through treatment of an adverse event.

In addition, an evaluation and possibly a change in the study protocol will be initiated due to safety concerns.

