8.2.2 Serious Adverse Events

Serious Adverse Event (SAE): An SAE is defined as an AE that meets one of the following conditions:

Death during the period of protocol defined surveillance

Life-threatening event (defined as a subject at immediate risk of death at the time of the event)

An event requiring inpatient hospitalization or prolongation of existing hospitalization during the period of protocol defined surveillance

Results in a persistent or significant disability/incapacity

Any other important medical event that may not result in death, be life threatening, or require hospitalization, may be considered a serious adverse experience when, based upon appropriate medical judgment, the event may jeopardize the subject and may require medical or surgical intervention to prevent one of the outcomes listed above. Examples of such medical events include allergic bronchospasm requiring intensive treatment in an emergency room or at home, blood dyscrasias or convulsions that do not result in inpatient hospitalization, or the development of drug dependency or drug abuse.

All SAEs will be:

- recorded on the appropriate SAE source document
- followed through resolution by a study clinician
- reviewed and evaluated by a study clinician

8.2.3 Procedures to be followed in the Event of Abnormal Laboratory Test Values or Abnormal Clinical Findings

Bleeding will be closely monitored in the NICU setting. Daily CBC's are obtained during the postoperative period, and these will be recorded as data relevant to the study. Deviations in hemoglobin or platelet counts will be detected, and treated as is standard of care. If concern arises about the drug, the patient will be unblinded and pulled from receiving the study drug or placebo. However, events will still be recorded on the patient. Collection of laboratory data should be limited to those laboratory parameters that are relevant to safety, study outcome measures, and/or clinical outcome.

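### Sections 5.3.3 and 6.3 remove an infant from the study after a renal or bleeding event, while 5.3.4 and 8.2.3 stop only study product, so observation after a primary event is not clearly secured

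*Protocol*

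**What the plan says.** Four protocol sections describe what happens to an infant after a bleeding or renal event.

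- **5.3.3** introduces two renal criteria (low urine output over 8 hours; a 25% fall in estimated creatinine clearance) with: "Based upon the following criteria, a patient will be unblinded and pulled from the study".
- **6.3** covers both bleeding and acute renal change. Such infants "will not have dose modification, but will be pulled from the study". For the definition it points to a Section 5.2.3, which is not in the text: 5.2 is the list of exclusion criteria and has no subsections.
- **5.3.4** ends study product only: "The patient will become unblinded and pulled from receiving the study drug or placebo if any bleeding events occur or if renal function worsens", where worsening is given as a rise above 0.5 mg/dL. It then adds: "However, events will still be recorded on the patient, and these patients will still be followed for the duration of the study".
- **8.2.3**, triggered when concern arises about the drug, says "the patient will be unblinded and pulled from receiving the study drug or placebo. However, events will still be recorded on the patient".

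Three further sections bear on later observation. Section 7.2 allows for an early stop because of an AE and sets 48 hours of follow-up after the drug or placebo ends. Section 8.1 collects events over the same window. Section 8.2.1 follows AEs until they resolve. Section 3.2.1 names bleeding events and renal injury as the primary outcomes, and 8.1 defines renal injury by the same two criteria that 5.3.3 uses for removal.

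**The concern.** The events that trigger removal are the trial's primary outcomes. If removal means leaving the study, observation ends because of the outcome, and it ends in the infants about whom a safety trial most needs data. Still to be observed in such an infant would be the other primary outcome, a recurrence, the recovery of renal function or hemoglobin, and the section 3.2.2 measures (creatinine, opioid use, ventilator days, reintubation and others). If one arm had more first events, that arm would also lose more observation time. Staff who act on 6.3 and staff who act on 5.3.4 would collect different data on the same infant.

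**Working it through.** The protocol gives no figure to reproduce here. The check is a comparison of the sections, followed by arithmetic for scale.

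**1. What each section does after the event**

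| Section | Trigger | Infant leaves | Stated observation afterwards |
|---|---|---|---|
| 5.3.3 | Urine output or 25% clearance criterion | Study | None stated |
| 6.3 | Bleeding episode or acute renal change | Study | None stated |
| 5.3.4 | Bleeding, or rise above 0.5 mg/dL | Study product | Followed for the study duration |
| 8.2.3 | Concern about the drug | Study product | Events recorded |

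The first two rows and the last two cannot both govern the same infant, and no section gives an order of precedence.

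**2. Does 5.3.4 cover the infants removed under 5.3.3?** Not clearly, because the renal triggers differ. Assume that the rise in 5.3.4 is in serum creatinine, that the exclusion limit of 0.4 in section 5.2 is in mg/dL, and that clearance is inversely proportional to creatinine.

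- A 25% fall in clearance from baseline *b* needs creatinine *b*/0.75. At the highest permitted baseline, 0.4/0.75 = 0.53, a rise of 0.13.
- A rise of 0.5 takes 0.4 to 0.9, a clearance fall of 1 − 0.4/0.9 = 56%.

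So an infant starting at 0.4 and reaching a creatinine between about 0.53 and 0.9 meets 5.3.3, and the 8.1 definition of renal injury, without reaching the threshold in 5.3.4. At a lower baseline the required rise (*b*/3) shrinks while 0.5 stays fixed, so the gap widens. An infant with low urine output alone is also outside the 5.3.4 threshold.

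**3. Observation time at stake.** Planned follow-up is 5 days = 120 h. Count from the first dose.

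| Product stopped at | 5.3.3/6.3 literally | 7.2 (48 h after stop) |
|---|---|---|
| 24 h | 120 − 24 = 96 h lost (80%, 4 days) | 120 − 72 = 48 h lost (40%, 2 days) |
| 48 h | 120 − 48 = 72 h lost (60%, 3 days) | 120 − 96 = 24 h lost (20%, 1 day) |

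Section 5.3.4 gives two end points, 5 days or 72 h after study drug. For a stop at 24 h these are 120 h and 96 h, so it loses between 0 and 24 h.

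**4. How many infants.** Section 2.3.1 gives 1–3% for bleeding and 1–3% for renal insufficiency. Assume that the two do not overlap, so the rates add to 2–6%. Expected number = N × p; chance of at least one = 1 − (1 − p)^N.

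- All 50 infants: 1.0 to 3.0 expected; chance of at least one 64% to 96%.
- Ketorolac arm only (25): 0.5 to 1.5 expected; 40% to 79%.
- With the 60 given in the protocol summary: 1.2 to 3.6 expected; 70% to 98%.

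The rates are stated as risks of ketorolac, so applying them to all 50 assumes that they also hold on placebo. The protocol gives no rate for the 5.3.3 renal criteria themselves.

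**The case against.** The strongest reply is that the protocol, read as a whole, keeps these infants under observation. Section 5.3.4 directly follows 5.3.3 and is the section that most plainly addresses data after removal. Section 6.3 concerns dose modification and sets no rule on data collection. Section 7.2 foresees an early stop for an AE, 8.1 collects events including both renal criteria for 48 hours, and 8.2.1 follows AEs to resolution. Section 8.2.3 also foresees laboratory collection for parameters relevant to safety and the outcome measures. On this view the wording in 5.3.3 and 6.3 is loose shorthand for stopping the drug.

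Much of this stands. A reader might infer that all outcome data are lost after a first event, or that 60–80% of follow-up disappears. The documents do not support that as a general statement: it follows only if 5.3.3 and 6.3 are read in isolation. Nor does 5.3.3 remove infants from the study for bleeding; the removal sentence there introduces renal criteria only, and the bleeding half rests on 6.3. A second primary event of the other type would also be rare: at 1–3% each and assuming independence, 50 × 0.01² = 0.005 to 50 × 0.03² = 0.045 infants would have both, and more if the two are correlated.

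What does not stand is that the other sections settle the matter. Sections 7.2, 8.1 and 8.2.1 do not say that they apply to an infant who has been taken off the study, and following an AE to resolution is not the same as collecting opioid use, pain scores or ventilator days. The cross-reference in 6.3 leads nowhere, so it cannot tie 6.3 to 5.3.4.

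**Conclusion.** The contradiction is real, and the documents do not resolve it. The triggering event is recorded on every reading; the data at risk are those that come after it. For a stop on day 1 or 2 the possible loss runs from about 4 or 3 of 5 days (literal reading) to about 2 or 1 (if 7.2 applies). It would affect perhaps 1 to 3 of 50 infants at the protocol's own rates, under the assumptions stated above. These are few infants, but they are the ones with a primary safety event.

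A reader might go further and conclude that the arm comparison is biased. That would need both the literal reading and an excess of events in one arm; the protocol establishes neither, and section 10.2 disclaims statistical inference for this pilot. The point is therefore an inconsistency that should be fixed, not a defect that invalidates the trial.

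**What to change.** Reconcile 5.3.3, 5.3.4, 6.3, 7.2 and 8.2.3 so that stopping study product and leaving the study are two distinct things.

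1. In 5.3.3 and 6.3, replace the removal from the study with wording that ends study product only.
2. Correct the cross-reference in 6.3.
3. State once, and refer to it elsewhere, that unless consent is withdrawn every infant stopped for any listed reason remains under observation for both primary outcomes and all 3.2.2 measures to the end of the planned study period.
4. Give that end point once: 5.3.4 has 72 hours after study drug, while sections 4, 7.2 and 8.1 have 48.

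All four sections on removal already end study product, so none of this changes a dose or a stopping trigger. The renal triggers in 5.3.3 and 5.3.4 differ, and the sponsor must reconcile them; this review takes no position on which is right. How stopped infants are analyzed can be left to the SAP.

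The cost is a wording amendment with the IRB approval that section 11.2 requires. Section 7.1 describes the daily laboratory tests as routine postoperative care and already has the clinical measures recorded, so no new procedure is needed.

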4 STUDY DESIGN

This is a Phase II, single center, randomized controlled pilot study. Hospitalized patients one week of age to 3 months of age who undergo an abdominal or thoracic surgical procedure within the moderate or severe degree of pain category (see attached Table 1: postoperative pain categories) will be randomized to receive standard pain management regimens plus placebo (0.9% saline of equivalent volume) or ketorolac 0.5mg IV q8h x 72h plus standard pain management regimens. The postoperative management will be unchanged and at the discretion of the attending surgeon, as appropriate for the surgical procedure. The patients will be followed for 5 days, or 48hrs from the end of ketorolac therapy for primary and secondary endpoints. Ketorolac will be started within 24hrs of the end of the operative procedure.

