7.2 Follow-up

The drug/placebo will be administered every 8 hours for 72 hours, unless the medication is stopped earlier due to an AE. Patients will be followed for 48 hours from the completion of the drug/placebo administration. After 48 hours, the study will be concluded for that patient. There will be no further follow-up evaluations or visits.

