8 STUDY PROCEDURES/EVALUATIONS

8.1 Specification of Safety Parameters

Events will be collected during the duration of the study, which is 48 hours from the completion of the study drug/placebo.

Bleeding episodes will be defined by following:

- Persistent bloody drainage from a nasogastric tube, resulting in a drop of hemoglobin of greater than or equal to 2g/dL (change of 1g/dL in hemoglobin may be explained by the infusion of perioperative crystalloid, and in the absence of hemodynamic instability would be considered within the acceptable standard deviation)
- Surgical site bleeding resulting in a drop of hemoglobin $>2\text{g/dL}$ from initial postop value, unless the patient has required crystalloid or fluid boluses other than PRBC totalling 60ml/kg or greater.
- Any hemodynamic instability associated with a drop of hemoglobin $>2\text{g/dL}$

2. Renal injury will be defined by the following:

- Patients who are resuscitated but with continued postoperative $\text{UOP} < 0.5\text{ml/kg/h}$ persistent over 8 hours
- A decrease in estimated creatinine clearance by 25%, in a well-resuscitated patient

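### Infants stopped for a primary event are either off the study or only off drug, depending on the section, and clocks tied to the end of drug can shorten their observation

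*Protocol*

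**What the plan says.** **Status after a primary event.** Section 3.2.1 names bleeding events and renal injury as primary outcomes. Four sections say what happens when one occurs:

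- 5.3.3, for the renal criteria: "a patient will be unblinded and pulled from the study".
- 6.3, for a bleeding episode or an acute renal change: the infant "will not have dose modification, but will be pulled from the study".
- 5.3.4, for any bleeding event or a rise above 0.5 mg/dL: the infant comes off study drug, events continue to be recorded, and the infant will "still be followed for the duration of the study (i.e. 5 days or 72 hrs from the end of the study drug"), or until the adverse event resolves or is treated.
- 8.2.3: "the patient will be unblinded and pulled from receiving the study drug or placebo. However, events will still be recorded on the patient".

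**Length of follow-up.**

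- Section 4: "The patients will be followed for 5 days, or 48hrs from the end of ketorolac therapy for primary and secondary endpoints".
- 7.2 says dosing runs 72 h "unless the medication is stopped earlier due to an AE. Patients will be followed for 48 hours from the completion of the drug/placebo administration". It then adds: "After 48 hours, the study will be concluded for that patient. There will be no further follow-up evaluations or visits".
- 8.1: "Events will be collected during the duration of the study, which is 48 hours from the completion of the study drug/placebo".
- The Protocol Summary and section 5 give five days of participation without reference to when drug ends.

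**The concern.** The same infant gets different instructions in different sections, and the infants concerned are those with a primary event. Under 6.3 as written, observation ends at about the time of stopping. Under 7.2 and 8.1 it ends 48 h after drug ends, so the earlier the stop, the shorter the window.

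The event that led to stopping is counted under every reading. At stake is what follows it: the other primary outcome (renal injury after a bleed, or a bleed after renal injury) and the secondary outcomes in 3.2.2, such as creatinine, opioid amount, pain scores and ventilator days. The primary outcomes cause the stop, so the loss falls more on whichever arm has more harm. In a trial meant to characterise safety, that tends to hide later harm in the worse arm. An analysis plan cannot restore observations that the protocol did not have collected.

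**Working it through.** **Inputs.** Dosing every 8 h for 72 h, nine doses (6.2). Follow-up of 48 h after drug (4, 7.2, 8.1), 72 h after drug (5.3.4), or 5 days (4, 5.3.4). Creatinine above 0.4 excludes (5.2), taken here as mg/dL. Hours are counted from the first dose. The protocol does not state where its 5 days start, so the first dose is an assumption.

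**The plan's own figure.** For a completer, 72 + 48 = 120 h = 5 days, so the two limbs of section 4 agree. Counted from the ninth dose at 8 × 8 = hour 64, the window ends at 64 + 48 = hour 112.

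**When the limbs disagree.** Section 4's limbs agree only if drug ends at 120 − 48 = hour 72. Those of 5.3.4 agree only if drug ends at 120 − 72 = hour 48. For a completer, the 72 h limb gives 72 + 72 = 144 h, or 6 days, against the 5 days in the same bracket.

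**Early stoppers.** After n doses the last dose is at 8(n − 1). The window ends at 8(n − 1) + 48 or 8(n − 1) + 72. On the 48 h rule the gap to a completer is 8(9 − n).

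| Doses given | Last dose (h) | 48 h rule ends (h) | 72 h rule ends (h) | 5-day rule ends (h) | 48 h rule: gap to completer at hour 112 (h) | 48 h rule: gap to hour 120 (h) |
|---|---|---|---|---|---|---|
| 1 | 0 | 48 | 72 | 120 | 64 | 72 |
| 3 | 16 | 64 | 88 | 120 | 48 | 56 |
| 6 | 40 | 88 | 112 | 120 | 24 | 32 |
| 9 | 64 | 112 | 136 | 120 | 0 | 8 |

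Each dose not given costs 8 h on the 48 h rule. The 48 h gap after three doses is about two daily laboratory sets. Under 6.3 read literally, observation stops at about the time drug stops.

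**Does 5.3.4 cover everyone removed under 5.3.3?** Assume clearance is proportional to 1/creatinine. From the entry ceiling of 0.4, a 25% fall in clearance (5.3.3, 8.1) is reached at 0.4/0.75 = 0.53 mg/dL, a rise of 0.13. If the 0.5 mg/dL rise in 5.3.4 refers to creatinine, it means passing 0.4 + 0.5 = 0.9 mg/dL, where clearance has fallen by 1 − 0.4/0.9 = 56%. An infant between 0.53 and 0.9, or one who meets only the urine-output criterion, is removed under 5.3.3 but does not meet the stated renal trigger of 5.3.4.

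**How many infants.** Section 2.3.1 quotes population risks of 1–3% for bleeding and 1–3% for renal insufficiency. Simply added, they give 2–6%, or 0.02 × 25 = 0.5 to 0.06 × 25 = 1.5 ketorolac infants (25 per arm, 5.3.1). At an assumed stopping rate of 10–20% the number is 2.5 to 5. That rate is illustrative and has no basis in the protocol.

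**The case against.** Section 5.3.4 is the most detailed rule on stopping. It says plainly that the infant is still followed, and 8.2.3 repeats that events are still recorded. Neither 5.3.3 nor 6.3 says that data collection ends, and 6.3 deals with dose modification, so its phrase may be loose wording for stopping the drug. The Protocol Summary and section 5 give five days outright, which suggests that 48 h is only a completer's arithmetic. In 7.2 the words on early stopping qualify the dosing sentence, and completion could mean completion of the planned course. Daily blood counts and chemistry are routine care, 7.1 allows extra testing when bleeding or renal injury appears, and few infants are involved.

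Much of this stands as evidence of intent: five days with continued follow-up was probably meant. It also stands that many later laboratory values will exist in the hospital chart. The conflict remains. Section 7.2 mentions stopping for an adverse event, then applies 48 h and closes the study for that infant. Section 5.3.4 does not reach every infant removed under 5.3.3, and its own two limbs disagree for most stopping times. Following open adverse events to resolution (8.2.1, 8.2.2) does not extend collection of new events or secondary outcomes. Values left in a chart after the study has closed for an infant are not trial data unless the protocol says to collect them.

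**Conclusion.** The concern holds and should be fixed. The protocol gives incompatible instructions on whether an infant with a primary event stays in the study and for how long. Only the 5-day reading gives the full window at every stopping time. Against 120 h from first dose, the shortfall on the 48 h rule is up to 72 h, and under a literal 6.3 almost the whole window can go. The 72 h rule falls short only when drug ends before hour 48.

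The number of infants affected is probably small, and the neonatal rate is not known. The direction of the loss, towards the arm with more stops, follows from tying observation to the outcome. The size of any resulting bias cannot be computed from the protocol. The conflict in the text is certain. How much data would be lost depends on which section staff follow.

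**What to change.** - In 5.3.3 and 6.3, replace removal from the study with: study drug stops, and the infant stays in the study and is followed. This matches 5.3.4 and 8.2.3.
- In 4, 5.3.4, 7.2 and 8.1, set one window of 120 h from first dose for every randomised infant, whenever drug stopped. Extend it only to follow unresolved adverse events. The shortfall is then 0 h at any stopping time.
- In the same edit, give 5.3.3 and 5.3.4 one renal stopping criterion, and correct the cross-reference in 6.3, which points to a section 5.2.3 although the definitions are in 5.3.3.

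The cost is wording in six sections. For an early stopper the added chart abstraction is at most 72 h compared with the 48 h rule, and up to about 120 h compared with a literal 6.3. It draws on daily laboratory tests that 7.1 already treats as routine, and it fits the five-day participation already stated.
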